7.4 Sample Size, Effect Size, and Accrual

The combined targeted event rate (HIV infections and Death) in the detoxification arm at 104 week is 12.5% HIV infected or dead, assuming 8.5% due to HIV infection and 4% from death. The hypothesized treatment effect is a 50% reduction in the proportion of HIV-1 infections and a 25% reduction in the proportion of deaths observed in the substitution arm relative to the detoxification arm at 104 weeks. The combined targeted event rate in the substitution arm at 104 weeks is therefore 7.25% HIV infected or dead.

In the proposed sites, projected annual seroincidence rates among injectors per 100 person years are 3.0 in Chiang Mai, 3.1 in Guangxi, and 8.8 in Xinjiang. Using enrollment ratios that favor the highest incidence site we project a baseline seroincidence rate of 5.4 per 100 person years.

Risk reduction counseling is expected to be 20% effective in reducing HIV infections but have no effect on deaths. The rate of infection at 2 years in the detoxification arm is thus calculated as 1 – (1-0.054*0.8) ²=0.085. This 20% overall reduction also accommodates the possible entry into methadone treatment in a small proportion of participants in the detoxification arm. The study team and oversight committees (SMC, DSMB) will closely monitor the number of participants in each arm of the study who enroll in methadone maintenance programs. Depending on the extent of methadone uptake in the study population, the sample size and power calculations could be adjusted, if necessary.

In Thailand, a mortality rate of 2.33 per 100 person years was observed in the OUR study. Among IDUs in Northern Thailand followed in HPTN037, the mortality rate was 4.0 (2.3-6.4) per 100 person-years. In HPTN 033, death rates of 1.68 and 0.44 were observed among IDUs in Xinjiang and Guangxi, respectively. Death rates are targeted at 4% at two years, based on a rate close to 2.0 per 100 person years.

Mortality has been reported to decrease as a result of effective treatment for opioid use among IDUs. ^{137, 138} Analysis of the efficacy endpoint of HIV-free survival is free of the bias induced by the informative censoring that would result if HIV incidence were the primary endpoint and deaths were censored. Thus HIV free survival is chosen as the primary efficacy analysis for this intervention. Nonetheless, prevention of HIV infection remains a primary focus of the evaluation, and analysis of HIV infection rates will be an important secondary analysis.

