7.4.1 Sample Size

To achieve 90% power for reduction in the probability of HIV infection or death at 104 weeks from 12.5% to 7.25% requires a total of 1345 participants, based on a normal approximation for testing the difference in binomial proportions, assuming variance under the alternative, and one-sided alpha of 0.025. Allowing for loss to follow-up at 104 weeks of 10%, a projected total enrollment of 1500 (750 participants per arm) is required.

A total enrollment of 1500 will yield an approximate sample of 1290 for the HIV-free survival endpoint, assuming an additional 4% loss to follow-up attributable to censoring due to death. The power for the HIV infection endpoint is given below for a range of potential rates for HIV infection, assuming 50% efficacy for the HIV infection endpoint.

Power for the HIV infection Endpoint.							
Substitution Arm Detoxification arm Power							
3.5%	7.0%	92.8					
4.25%	8.5%	88.0					
5.0%	10.0%	80.7					

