7.7.2 Secondary Analyses

- 1. To determine if the substitution treatment reduces average HIV incidence and death compared to the detoxification arm; and reduces HIV incidence and death at 52 weeks and 156 weeks.
- 2. To determine if the substitution treatment decreases average HIV incidence compared to the detoxification treatment; and decreases HIV incidence at 52, 104, and 156 weeks.
- 3. To compare the average rates of deaths between the two arms; and the rates of death at 52, 104, and 156 weeks.
 - For each of the above three endpoints, "average" rates will be compared between treatment arms using a log-rank test, which utilizes all the event information accumulated in the trial. Rates will then also be compared for the specified time points using Kaplan Meier estimates of the proportion uninfected after the 52, 104 and 156 week visits, and with variances estimated by Greenwood's formula.
- 4. To compare the self-reported frequency of injection, drug and sex-related HIV risk behaviors in the two study arms.
 - Self reported behaviors will be analyzed using generalized estimating equations techniques for repeated measures of behavior to assess difference in frequency of use between the two study arms.
- 5. To compare the frequency of drug use measured by self-report and by urinalysis in the two study arms.
 - Urinalysis results will be compared between arms using simple cross sectional summaries at each time point, in addition to generalized estimating equation approaches for repeated measures. In addition, comparison between urinalysis and self-reported injection frequency will be used to assess validity of self reported data.

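### The HIV-only Kaplan-Meier estimates censor deaths and so slightly overstate the proportion actually infected; a cumulative incidence should stand beside them

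*Protocol*

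**What the plan says.** Protocol 7.4 makes HIV-free survival the primary endpoint because it avoids "the informative censoring that would result if HIV incidence were the primary endpoint and deaths were censored". The same paragraph keeps HIV alone in view: "analysis of HIV infection rates will be an important secondary analysis".

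Protocol 7.7.2 fixes the method for its first three items: HIV or death, HIV alone, and death alone. Average rates are compared by log-rank test. After that, "Rates will then also be compared for the specified time points using Kaplan Meier estimates of the proportion uninfected" at 52, 104 and 156 weeks, with Greenwood variances.

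Section 7.7.2 does not say how a death enters the HIV-only curve. Section 7.4.1 does so for the sample calculation: it goes from 1500 enrolled to about 1290, "assuming an additional 4% loss to follow-up attributable to censoring due to death". That sentence labels the 1290 as belonging to HIV-free survival. Taking deaths out, and the power table that follows, show that it serves the HIV infection endpoint.

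The planned rates are in 7.4. For the detoxification arm at 104 weeks they are "assuming 8.5% due to HIV infection and 4% from death". The hypothesised effect is "a 50% reduction in the proportion of HIV-1 infections and a 25% reduction in the proportion of deaths". The sensitivity analysis in 7.7.1 concerns participants lost to follow-up, not deaths.

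**The concern.** A participant who dies uninfected cannot become infected later. Censoring that death makes Kaplan-Meier treat the person as still open to infection at the rate of those who remain. One minus the estimate is then a hypothetical risk in a population where nobody dies, and it always exceeds the proportion who in fact become infected. Section 7.7.2 presents the result as a proportion, and 7.4 states the hypothesised effect as a reduction in a proportion, so readers will take it as an absolute risk and derive infections prevented from it.

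A second, distinct issue is the one that 7.4 raises: if those who die differ in HIV risk from those who survive, the censoring is informative and the no-death risk is itself misestimated. The HIV-only result is the most prominent secondary result, and both gaps depend on mortality, which in this population is not negligible.

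**Working it through.** **The plan's own figure.** 1500 x (1 - 0.10 - 0.04) = 1290, or 645 per arm. For 8.5% v 4.25%, with variance under the alternative and one-sided alpha 0.025:

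- Standard error = sqrt[(0.085 x 0.915 + 0.0425 x 0.9575)/645] = 0.01355.
- 0.0425/0.01355 = 3.136, so power = Phi(3.136 - 1.960) = 88.0%.

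This matches the middle row of the table in 7.4.1, so the plan's calculation does take deaths out of the HIV-only sample.

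**Inputs for the comparison (7.4), at 104 weeks.** HIV 8.5% in the detoxification arm and 8.5% x 0.5 = 4.25% in the substitution arm. Deaths 4% and 4% x 0.75 = 3%. Assumptions: constant hazards, independence of the two causes, and the HIV figures read as risks with deaths removed.

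**Formulas.** For each arm, h = -ln(1 - HIV risk)/2 and d = -ln(1 - death risk)/2 per year.

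- One minus Kaplan-Meier, deaths censored: 1 - exp(-h t).
- Cumulative incidence, death competing: [h/(h + d)] x [1 - exp(-(h + d) t)].

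**At t = 2 years.**

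- Detoxification: h = 0.04442, d = 0.02041. Cumulative incidence = (0.04442/0.06483) x 0.1216 = 8.33%, against 8.50% by Kaplan-Meier.
- Substitution: h = 0.02171, d = 0.01523. Cumulative incidence = (0.02171/0.03694) x 0.0712 = 4.19%, against 4.25%.

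Differences between arms, in percentage points (last digits may differ by one through rounding; percentages are relative to the cumulative incidence difference):

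| Deaths, detoxification v substitution | Week | Kaplan-Meier | Cumulative incidence | Excess |
|---|---|---|---|---|
| 4% v 3% | 52 | 2.196 | 2.169 | 0.027 (1.3%) |
| 4% v 3% | 104 | 4.250 | 4.145 | 0.105 (2.5%) |
| 4% v 3% | 156 | 6.168 | 5.943 | 0.226 (3.8%) |
| 4.0 v 3.0 per 100 person-years | 104 | 4.250 | 4.048 | 0.202 (5.0%) |
| 4.0 v 3.0 per 100 person-years | 156 | 6.168 | 5.737 | 0.431 (7.5%) |
| 4% v 4% | 104 | 4.250 | 4.166 | 0.084 (2.0%) |
| 4% v 8% | 104 | 4.250 | 4.252 | -0.002 |
| 4% v 9% | 104 | 4.250 | 4.274 | -0.024 |

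The rate of 4.0 per 100 person-years is the Northern Thailand figure quoted in 7.4; the substitution-arm rate is taken 25% lower.

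With equal deaths, 0.084 of the 0.105 points remains, so most of the excess comes from the higher HIV rate in the detoxification arm. It disappears when substitution-arm deaths are about double those in the detoxification arm, and reverses beyond that.

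**The other reading of the inputs.** Section 7.4 adds 8.5% and 4% to reach 12.5%, which suits mutually exclusive proportions. Two independent net risks would give 1 - 0.915 x 0.96 = 12.2%. If 8.5% and 4.25% are instead the proportions actually infected, Kaplan-Meier would show a difference of 4.36 points against 4.25, so the excess is again about 0.11.

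**Informative censoring.** A simulation let HIV and death share a gamma frailty, with net risks held at plan. The variances 1, 3 and 6 are assumptions.

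| Frailty variance | Net difference | Kaplan-Meier | Cumulative incidence |
|---|---|---|---|
| 1 | 4.25 | 4.16 | 4.06 |
| 3 | 4.25 | 4.02 | 3.93 |
| 6 | 4.25 | 3.87 | 3.80 |

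In the detoxification arm Kaplan-Meier falls from 8.35% to 7.83% across these variances, against a net risk of 8.50%. It lies below the net risk and above the cumulative incidence, so it equals neither.

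**The case against.** The strongest reply has four parts.

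- **The team saw the problem.** It made the composite primary for this reason and kept HIV alone as secondary knowingly. Deaths are also analysed on their own in 7.7.2 item 3. This stands, and it is why the primary result is untouched.
- **The effect is small.** An excess of 0.105 points is about 0.08 of the standard error of 1.36 points, and the risk ratio moves from 0.500 to 0.503. This stands too.
- **Kaplan-Meier and the log-rank test answer a legitimate question about the infection rate among those alive.** Cumulative incidence mixes in survival. With no HIV effect and deaths of 4% v 3%, Kaplan-Meier shows no difference, while cumulative incidence shows substitution 0.04 points worse only because more of its participants live. This is a good reason not to replace Kaplan-Meier outright.
- **A competing-risk estimate could be left to the analysis plan.** This stands only in part: 7.7.2 names a method, and what it names does not give the proportion infected.

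A reader might also infer that 7.4 itself condemns the overstatement computed here. It does not. It speaks of informative censoring, whereas the gap in the first table arises with independent causes. Nor does a link between death risk and HIV risk add to the overstatement: in the simulation the excess over cumulative incidence at 104 weeks shrinks from 0.105 to about 0.07 points.

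**Conclusion.** The point holds as a modest improvement to a secondary analysis. As an estimate of the proportion infected, one minus Kaplan-Meier with deaths censored is always too high. At planned rates the arm difference is too high by about 0.1 point at 104 weeks and 0.2 at 156 weeks, or roughly twice that at 4.0 deaths per 100 person-years. These sizes rest on constant, independent hazards. That deaths are censored in the HIV-only curve is taken from 7.4.1, since 7.7.2 is silent. If those who die have higher HIV risk, which is an assumption the protocol does not quantify, Kaplan-Meier also understates the net risk.

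The documents do not support two stronger readings: that the bias exists only because deaths are expected to differ by arm, or that it endangers the trial's conclusion. The primary composite is unaffected, and the log-rank test remains valid as a cause-specific comparison.

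**What to change.** In 7.7.2 item 2, add one sentence: the absolute risk of HIV infection at 52, 104 and 156 weeks will be estimated in each arm by cumulative incidence with death as a competing event, using the Aalen-Johansen estimate and its variance. Keep the log-rank test. Keep Kaplan-Meier, and state that it gives the risk with deaths censored.

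No new data are needed and the software is standard. Power does not suffer: keeping deaths in the denominator (1500 x 0.90 = 1350, or 675 per arm), 8.33% v 4.19% gives 88.4%, against 88.0% in the plan. The cost is one more set of estimates. Because cumulative incidence also reflects survival differences between arms, it should be read beside the death results in item 3.

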7.4.1 Sample Size

To achieve 90% power for reduction in the probability of HIV infection or death at 104 weeks from 12.5% to 7.25% requires a total of 1345 participants, based on a normal approximation for testing the difference in binomial proportions, assuming variance under the alternative, and one-sided alpha of 0.025. Allowing for loss to follow-up at 104 weeks of 10%, a projected total enrollment of 1500 (750 participants per arm) is required.

A total enrollment of 1500 will yield an approximate sample of 1290 for the HIV-free survival endpoint, assuming an additional 4% loss to follow-up attributable to censoring due to death. The power for the HIV infection endpoint is given below for a range of potential rates for HIV infection, assuming 50% efficacy for the HIV infection endpoint.

Power for the HIV infection Endpoint.							
Substitution Arm Detoxification arm Power							
3.5%	7.0%	92.8					
4.25%	8.5%	88.0					
5.0%	10.0%	80.7					

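### The HIV-infection power table in Section 7.4.1 has its outer power values exchanged, and its sample of 1290 carries the primary endpoint's name

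*Protocol*

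**What the plan says.** Protocol Section 7.4.1 sizes the trial on the primary endpoint: "reduction in the probability of HIV infection or death at 104 weeks from 12.5% to 7.25% requires a total of 1345 participants" at 90% power, "based on a normal approximation for testing the difference in binomial proportions, assuming variance under the alternative, and one-sided alpha of 0.025". It continues: "Allowing for loss to follow-up at 104 weeks of 10%, a projected total enrollment of 1500 (750 participants per arm) is required".

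The next paragraph says that enrolling 1500 people "will yield an approximate sample of 1290 for the HIV-free survival endpoint, assuming an additional 4% loss to follow-up attributable to censoring due to death", and introduces a table: "The power for the HIV infection endpoint is given below for a range of potential rates for HIV infection, assuming 50% efficacy". The table reads:

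| Substitution | Detoxification | Printed power (%) |
|---|---|---|
| 3.5% | 7.0% | 92.8 |
| 4.25% | 8.5% | 88.0 |
| 5.0% | 10.0% | 80.7 |

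The middle row is the planning case of Section 7.4, which builds the detoxification-arm rate "assuming 8.5% due to HIV infection and 4% from death". Section 7.2.1 defines the primary endpoint as HIV-1 infection or death by the 104-week visit. Section 7.4 explains that censoring deaths would bias an HIV-only endpoint and concludes: "Thus HIV free survival is chosen as the primary efficacy analysis for this intervention".

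**The concern.** Two things in one paragraph do not fit.

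First, the direction of the table. Every row has the same relative effect and the same sample, and only the event rate changes. More events should give more power, yet printed power drops by 12.1 points from the lowest rate to the highest.

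Second, the label on the 1290. It is reached by removing a further 4% for deaths, on top of the 10% loss. Under HIV-free survival a death is an outcome and is not removed. As worded, the primary endpoint has fewer participants than the 1345 that the preceding paragraph requires.

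The low-incidence row is the one a reader needs. Section 7.4 projects 3.0, 3.1 and 8.8 infections per 100 person-years at the three sites and reaches 5.4 only by weighting enrolment to the highest. Section 1.2 reports much lower incidence in the HPTN 037 cohort in Chiang Mai and warns that wider methadone provision could reduce transmission. Inverting the protocol's own formula, a two-year rate of 7.0% corresponds to a baseline incidence of (1 − √0.93)/0.8 = 0.0445, or about 4.5 per 100 person-years. A modest shortfall from 5.4 therefore leads to the first row, where the table offers reassurance that is not there. Section 7.4 calls HIV infection an important secondary analysis, and this table is the protocol's only display of its power across rates.

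**Working it through.** **Inputs.** One-sided alpha 0.025, normal approximation, variance under the alternative, 10% loss and 1500 enrolled (all Section 7.4.1); 1:1 allocation (Section 7.5); 50% reduction and the three pairs of rates (Section 7.4.1). The alpha and variance form are stated for the primary calculation; I assume that they carry over to the table.

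**Reproducing the primary sample size.** n per arm = (z₀.₉₇₅ + z₀.₉₀)² × (p₁q₁ + p₂q₂) / (p₁ − p₂)².

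- Variance sum: 0.125 × 0.875 + 0.0725 × 0.9275 = 0.17662. Squared difference: 0.0525² = 0.002756.
- Full-precision z-values give 673.3 per arm, 1346.6 in total. Rounded z-values (1.96 + 1.28) give 10.4976 × 0.17662 / 0.002756 = 672.7 per arm, or 1345 in total. The stated figure reproduces.
- 1345 / 0.90 = 1494.4, so 1495, rounded up to 1500.

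**Which sample is which.** 1500 × 0.90 = 1350 after loss alone. 1500 × (1 − 0.10 − 0.04) = 1290 after loss and deaths, or 645 per arm.

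**Recomputing the table.** Power = Φ(|p₁ − p₂| / √((p₁q₁ + p₂q₂)/645) − 1.96).

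| Rates | p₁q₁ + p₂q₂ | SE | Difference / SE | Power (%) | Printed (%) |
|---|---|---|---|---|---|
| 3.5 vs 7.0 | 0.098875 | 0.01238 | 2.827 | 80.7 | 92.8 |
| 4.25 vs 8.5 | 0.118469 | 0.01355 | 3.136 | 88.0 | 88.0 |
| 5.0 vs 10.0 | 0.137500 | 0.01460 | 3.425 | 92.8 | 80.7 |

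All three printed values reappear to the decimal, with the outer two exchanged.

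**Why the printed order cannot be right.** With detoxification rate p and substitution rate p/2, difference / SE = (√n / 2) × √(p / (1.5 − 1.25p)). This increases with p at any fixed n, so no single sample size makes power fall as the rate rises.

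**Other methods.** Each gives power that rises with the rate (7.0%, 8.5%, 10.0%):

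- pooled variance: 80.5, 87.9, 92.7
- continuity correction: 77.1, 85.6, 91.3
- Schoenfeld on expected events: 83.3, 90.1, 94.3
- one-sided alpha 0.05: 88.1, 93.2, 96.2
- all 1500 enrolled: 86.2, 92.2, 95.8

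Holding the absolute difference at 4.25 points would reverse the order, but it gives 94.5, 88.0 and 81.1. Those are not the printed values, and every row of the table states a halving.

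**The label.** Because 1290 reproduces the HIV-infection powers, it is that endpoint's sample. For the primary rates (12.5% vs 7.25%), power is 90.1% with 1350 and 88.7% with 1290.

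**The case against.** The strongest reply concedes both slips and disputes what follows from them.

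- **No operational rule uses the table.** Sections 7.4 and 7.4.3 already direct enrolment to the higher-incidence sites, and Section 7.6 bases monitoring on O'Brien-Fleming boundaries and a separate plan. This largely stands. Section 7.4.3 does have site incidence reviewed about every three months, and Section 7.4 leaves power calculations open to adjustment, so the table could be consulted. But the protocol's other text points the right way, and I see no direct route to a wrong allocation. The firm harm is a false statement of power at low incidence.
- **The 88.7% is not a property of the plan.** The preceding paragraph sizes the primary endpoint properly, and the mention of deaths shows which endpoint was meant. This stands too. The figure shows only what the sentence says if taken at its word. Moreover, the primary analysis in Section 7.7.1 is intent-to-treat by Kaplan-Meier on the whole sample, so neither 1290 nor 1350 is a fixed analysis set.
- **The endpoint is secondary.** True, and the planning row is correct. That limits the reach of the error without removing it.

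A fault in reading the PDF is unlikely. Each row keeps its 2:1 ratio, the values are legible and the middle row matches.

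**Conclusion.** Both errors are real as printed. Power at 3.5% vs 7.0% is 80.7%, not 92.8%, and at 5.0% vs 10.0% it is 92.8%, not 80.7%: 12.1 points each, in opposite directions. The 1290 belongs to the HIV-infection endpoint; the primary endpoint has about 1350 after 10% loss and keeps 90.1% power. The corrected values assume that the table uses the alpha and variance form stated for the primary calculation, which the match in all three values supports. The reversed direction needs no such assumption. The primary sample size of 1345, the enrolment of 1500 and the planning row do not change. The error should be corrected because it overstates power in the low-incidence case, for an endpoint that the protocol treats as important.

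**What to change.** In the Section 7.4.1 table, print 80.7 for 3.5% vs 7.0%, keep 88.0 for 4.25% vs 8.5%, and print 92.8 for 5.0% vs 10.0%. In the sentence above it, replace HIV-free survival with HIV infection as the endpoint that has the sample of 1290. It would help to add that the corresponding number for HIV-free survival is 1350, and that the table uses the same alpha and variance form as the primary calculation.

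The cost is wording only, with no change to enrolment, endpoint or analysis. The sponsor does have to accept a less favourable figure: power for HIV infection falls to about 81% if the detoxification-arm rate is 7.0%.

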7.4.2 Effect Size

Effectiveness estimates for this trial were derived in part from two published placebo controlled randomized trials, one examining the effectiveness of buprenorphine and the other the effectiveness of methadone for treatment of opiate dependence.

A randomized, placebo controlled trial of one year of buprenorphine was conducted amongst 40 volunteers in Sweden, in 2000-1.¹³⁹ In the buprenorphine treatment arm, only one out of 20 people had no negative test results when testing for continued opiate use (i.e., never stopped using opiates). Of the remaining 19, about 80% of their samples were negative for opiates. In the control arm, 13 out of 20 had no negative samples, and of the remaining seven, about 50% of their samples were negative for opiates. ¹⁴⁰ Assuming reduction in injection translates directly to reduction in HIV infection, we estimate HIV infection rates after 1 year in the HPTN 058 study as:

$$rate_{drug} = \frac{1}{20} \times rate_{0} + \frac{19}{20} \times rate_{0} \times 0.20$$

$$rate_{csl} = \frac{13}{20} \times rate_{0} + \frac{7}{20} \times rate_{0} \times 0.50$$

In addition, we require for the substitution intervention to be considered effective that after a year off BUP/NX, it remains at least half as effective as when on BUP/NX. The detoxification arm is assumed to remain equally effective to provide the most conservative basis for comparison.

In the table below, one and two year cumulative HIV infection rates are presented based on these effectiveness assumptions derived from the Swedish study for baseline infection rates of 5 to 8 per 100 person years.

Annual infection rate	Proportion HIV Infected at 1 year Proportion HIV Infected at 2 years			% reduction is compared to be years		
Baseline	Substitution	ion Detox Substitution Detox		Detox	Substitution	Detox
8	1.9	6.6	6.1	12.8	60.3	16.9
7	1.7	5.8	5.3	11.2	60.4	17.0
6	1.4	5.0	4.6	9.7	60.6	17.1
5	1.2	4.1	3.8	8.1	60.7	17.1

A randomized controlled trial of long-term methadone treatment was conducted among 100 volunteers in Hong Kong in 1972-5. In the methadone study, after 3 years 5/50 subjects (10%) on methadone had 6 consecutive positive urine tests for morphine (the

condition for termination from study), while 31/50 subjects (61%) on placebo had 6 consecutive positive urine tests for morphine. After 32 weeks, 5 of the controls were still on placebo, whereas 38/50 (76%) remained on methadone treatment. At three years, 1/50 of control were still on placebo, and 28/56 (56%) on treatment, i.e., 49/50 no longer on placebo; 22/50 no longer on methadone. Among those on methadone, about 35% had at least one positive urine each month, and in those who were positive on a given month, about 10-20% of their daily urines were positive.

Using the results from this study, we derive the following estimates of potential effectiveness. For those on substitution treatment, 25% will fail to stay on treatment throughout the year, however their injection risk is still reduced by 50% during the year. The remaining 75% remain on treatment, with an average reduction in risk of 93%. For those receiving detoxification, we assume 10% reduce their risk by 100%, but among the remaining 90%, their injection risk is reduced by 10%. As above, we further assume that reduction in injection risk translates to reduction in HIV infection risk, and that the effectiveness of the first year continues in the detoxification arm, but is reduced by half in the substitution arm after weaning from BUP/NX.

The table below estimates 52 and 104 week cumulative HIV infection rates based on the effectiveness assumptions above derived from the methadone study for baseline infection rates of 5 to 8 per 100 person years.

Annual infection rate	Proportion H at 52 weeks	IV Infected	Proportion H at 104 weeks	IV Infected	% reduction in infection compared to baseline at 104 weeks		
Baseline	Substitution Detox		Substitution	Detox	Substitution	Detox	
8	1.4	6.5	5.3	12.5	65.4	18.4	
7	1.2	5.7	4.7	11.0	65.5	18.4	
6	1.1	4.9	4.0	9.5	65.7	18.5	
5	0.9	4.1	3.3	7.9	65.8	18.6	

The data from these protocols support the effect size estimates of 50% reduction in HIV infection at 2 years used in HPTN 058.

